Transdiagnostic group CBT vs. standard group CBT for depression, social anxiety disorder and agoraphobia/panic disorder (TRACT-RCT): A pragmatic, multicenter non-inferiority randomized controlled trial

Statistical Analysis Plan

Primary and secondary analyses

Version 2.0 2019.08.08

Introduction

This statistical analysis plan (SAP) describes the methods to be used to analyze the primary and secondary outcome data from the TRACT-RCT trial. The plan is based on the study protocol (Arnfred et al., 2017) registered at www.clinicaltrials.gov (Identifier: NCT02954731). Analyses follow the ICH-9 statistical guidelines for clinical trials and updated CONSORT reporting guideline extensions for non-pharmacological trials and non-inferiority and equivalence trials.¹⁻³

The statistical analysis plan will be open to adjustments after the blind review, however finalized and registered as an amendment to the study protocol before breaking the blind.

Research objectives and hypotheses

The use of a single transdiagnostic cognitive behavior therapy manual (i.e. The Unified Protocol for Transdiagnostic Treatment of Emotional disorders (UP))^{4,5} instead of several diagnosis-specific manuals for anxiety and depression disorders has the potential to simplify group logistics and reduce waiting time for patients. Applying the UP to heterogeneous groups might be a cost-effective way of delivering evidence-based psychological treatment for the most common mental disorders. While preliminary results for individual therapy with the UP for anxiety is promising, adaptations of the UP for depression and for group delivery need adequately testing.

The main objective of this study is to investigate the efficacy of group UP compared with standard diagnosis-specific cognitive behavior therapy (dCBT) for psychiatric outpatients with a primary diagnosis of unipolar depression, social anxiety disorder, panic disorder, or agoraphobia. Main outcome is subjective well-being measured with the World Health Organization Well-being Index, five items (WHO-5)⁶ post treatment. Other outcomes are symptom levels, personality traits, emotion regulation, perseverative thinking, social functioning and clients' evaluation of therapy.

We hypothesize that subjective well-being and symptom levels will be equally improved following group UP and group dCBT.

Apart from the main objective, we investigate the effects of the UP on emotion regulation, the role of possible mediators and moderators on outcome, as well as qualitative data on patients' and therapists' experience of psychotherapy. These analyses are specified elsewhere.

Study methods

Design

Please see study protocol (Arnfred et al., 2017)⁷ or www.clinicaltrials.gov (Identifier: NCT02954731).

Randomization

Please see study protocol (Arnfred et al., 2017)⁷.

Sample size

Please see study protocol (Arnfred et al., 2017)⁷.

Correction: In the study protocol we wrote that alpha was set to 5% resulting in a 95% one-sided confidence interval (CI). Following Trial guidelines^{1,8}, the alpha should be 0.025 resulting in a 97.5% one-sided CI. Further, standard deviation (SD) endpoint WHO-5 was reported to be 17.4 WHO-5 points. As reported in Reinholt et al. (2017)⁹ the correct WHO-5 endpoint SD is 20.44. Using these corrected values, then a sample size of 208 patients are required to be 90% sure that the lower limit of a one-sided 97.5% confidence interval (or equivalently a 95% two-sided confidence interval) will be above the non-inferiority limit of -9 WHO-points.

Due to an unexpected, high attrition rate within the first year of inclusion, we decided to adjust sample size calculations by increasing the number of included patients from in total 248 patients to in total 320 patients to get 204 participants completing the treatment as needed for the primary analysis based on our initial sample size calculations. The revised sample size calculation is documented in an amendment to the protocol at www.clinicaltrials.gov (Identifier: NCT02954731).

Timing of outcome assessments

Baseline characteristics will be assessed at the time of inclusion. Outcome measures will be assessed pre-treatment (up to two weeks before start of intervention), post treatment (week 19-21 after allocation), and at six months follow-up (45-47 weeks after allocation). The primary outcome (WHO-5) is further assessed at the beginning of each therapy session (14 sessions).

Timing of final analysis

Primary and secondary outcomes are analyzed post treatment and exploratively repeated at six months follow-up.

Statistical principles

Data presentation

We will analyze and report primary and secondary outcomes in accordance with CONSORT reporting guidelines for non-inferiority and equivalence trials.² Results from the primary analysis will be reported as between group mean differences with one-sided 97,5% confidence intervals. The focus will be on hypothesis testing rather than point estimation. For secondary analyses, results will be reported as within and between group mean differences with one-sided 97,5% confidence intervals. Effect sizes (Cohens *d*) are calculated for each measure between groups. A one-sided p-value < .025 is considered significant. The focus of secondary analyses will be on point estimation rather than hypothesis testing.

No adjustment for multiplicity will be undertaken. Since outcomes are interrelated, adjustment will be overly conservative.

Adherence and protocol deviations

We will analyze attrition rates (number of patients receiving less than 8 sessions of therapy) in both groups using Chi-square analysis.

The analysis population

In superiority trials, the Intention-to-treat (ITT) analysis is considered the conservative choice to minimize possible type I-errors, that is falsely concluding that the one treatment is superior to another.¹⁰ The ITT population includes all patients randomized and allocated to treatment whether they violated the protocol or dropped out of treatment or not. In superiority trials, the null-hypothesis asserts that there is no difference between the two interventions being compared. The alternative hypothesis being tested is that the two treatments are different by some prespecified value.

A non-inferiority trial, conversely, tries to show that a new treatment is not unacceptably worse than the treatment used for comparison by a prespecified margin.^{11,12} The null hypothesis states that the new treatment is worse than the reference treatment by more than a prespecified non-inferiority margin. In non-inferiority trials, the ITT analysis is conventionally considered a liberal choice because it tends to make the two treatments being compared more similar, possibly falsely inflating type I-errors, that is concluding that the new treatment is non-inferior to the reference treatment. Following CONSORT reporting guidelines, the PP population is, therefore, considered the conservative choice of analysis in non-inferiority trials.²

Given the potential biases in both PP and ITT analysis, the European Medicines Agency (EMA) in the paper *'Points to consider when switching between superiority and non-inferiority'* states that inference of non-inferiority should rely on both PP and ITT-analyses.⁸ Other authors (i.e. Sanchez & Chen, 2006¹³) argue that showing non-inferiority in both sets of analysis does not guarantee a valid conclusion as the conservatism or non-conservatism of the PP population depends on several factors, including the quality of the study, type of protocol violations and missingness. Sanchez & Chen (2006)¹³ recommend minimizing the impact of protocol violations and missingness in the statistical analysis by using a hybrid ITT/PP analysis which excludes non-compliant patients as in the PP population and properly addresses the impact of non-trivial missing data in an ITT analysis. We will use this hybrid model for analysis of primary and secondary outcomes.

For this analysis plan, the PP population is defined as patients completing the therapy (i.e. receiving eight therapy sessions or more). The ITT population is defined as all patients randomized and allocated to treatment.

Trial population

Eligibility

Please see study protocol (Arnfred et al., 2017)⁷ or www.clinicaltrials.gov (Identifier: NCT02954731).

Recruitment

Please see study protocol (Arnfred et al., 2017)⁷ or www.clinicaltrials.gov (Identifier: NCT02954731).

Participant flow

The number of patients screened, randomized, completed treatment, and completed follow-up outcomes, will be summarized in a CONSORT flow diagram.³

Baseline characteristics

The following demographic and illness burden variables will be summarized by treatment condition in Table 1: age, sex, immigrant status, marital status, level of employment, level of education, children living at home, comorbidity, previous psychological treatment, current medication, age of onset, previous episodes with primary diagnosis, previous hospitalization, and personality traits (Standardized Assessment of Personality Abbreviated Scale (SAPAS)).¹⁴

Analysis

Primary outcome

The primary outcome is self-reported subjective well-being measured with the WHO-5 assessed post treatment (19 weeks after allocation; single score continuous outcome).

Secondary outcomes

To avoid multiplicity of testing, the following outcomes were specified as secondary outcomes compared to the study protocol (Arnfred et al., 2017)⁷ after enrolling patients in the study but prior to data-analysis:

- General anxiety and depression symptoms assessed with the Hopkins Symptoms checklist (SCL-25)¹⁵ 19 weeks after allocation (single score continuous outcome)
- Observer-rated anxiety symptoms assessed with the Hamilton Anxiety Rating Scale (HAM-A6)¹⁶ 19 weeks after allocation (single score continuous outcome)
- Observer-rated depression symptoms assessed with the Hamilton Depression Rating Scale (HAM-D6)¹⁷ 19 weeks after allocation (single score continuous outcome)
- Self-reported impairment of functioning assessed with the Work and Social Adjustment Scale (WSAS)¹⁸ 19 weeks after allocation (single score continuous outcome)

Exploratory outcomes (depending on diagnosis)

The following outcomes were specified as exploratory outcomes compared to the study protocol (Arnfred et al., 2017)⁷ after enrolling patients in the study but prior to data-analysis:

- Panic Disorder Severity Scale (PDSS)¹⁹ assessed 19 weeks after allocation (single score continuous outcome).
- Liebowitz Social Anxiety Scale - Self-Report (LSAS-SR)²⁰ assessed 19 weeks after allocation (single score continuous outcome).
- Mobility inventory for Agoraphobia (MIA)²¹, avoidance scale assessed 19 weeks after allocation (single score continuous outcome).
- Beck Depression inventory-II (BDI)²² assessed 19 weeks after allocation (single score continuous outcome).
- HAM-A6 analyzed by diagnosis (agoraphobia/social anxiety disorder/panic disorder)
- HAM-D6 analyzed by diagnosis (depression)

Analysis methods

Descriptive analyses

Baseline equivalence for the two groups compared will be assessed descriptively. No formal significance testing will be conducted, since we assume that differences between randomized groups could have occurred by chance.

Inferential analyses

Inferential analyses will be based on between group comparisons of group UP versus group dCBT.

Primary analysis

The primary analysis will compare the estimated endpoint of the primary outcome (WHO-5) between UP and dCBT conditions post treatment (19 weeks from allocation) adjusted for baseline WHO-5 values, variables predictive for missing data, and stratification variables (i.e. site (Copenhagen, Risskov, Slagelse) and diagnosis (depression, social anxiety disorder, panic disorder/agoraphobia)), fitting treatment (UP or dCBT) as a fixed effects factor.

We will use a one-sided 97.5% CI interval approach to test non-inferiority between conditions. The one-sided 97,5% CI for the between group difference point estimate post treatment will be calculated. Non-inferiority of UP compared to dCBT will be accepted if the lower bound of the 97,5% CI lies within the prespecified non-inferiority margin of – 9 WHO points (see Figure 1). If non-inferiority is accepted, we will use a closed testing procedure to test for superiority of UP over dCBT (i.e. lower bound of the 97,5% CI lies above 0).

The model will be fitted using a multilevel, mixed linear regression model, which allow us to use all 16 WHO-5 outcomes and handle missing data within the model. We will use stratification variables (i.e. site and diagnosis) and baseline outcome variables and treatment as fixed factors. We will apply an unstructured covariance matrix to the random effects in the model. If the model does not converge, we will apply other covariance matrixes (i.e. autoregressive, heterogeneous, compound symmetry, etc.) to the model and choose the covariance matrix with the best fit according to the Akaike Information Criterion. Note: During the blind review of data it turned out that, due to the imputation method used, we were not able to run the analysis applying a unstructured covariance matrix to the random effects in the model as planned Using the Akaike Information Criterion, the autoregressive, 4th order (AR4) covariance matrix,

showed the best fit with the data. Accordingly, the multilevel, mixed linear regression model were run applying the AR4 covariance matrix to the random effects in the model.

Secondary analyses

For secondary analyses we will use ANCOVA to test for non-inferiority between treatment conditions post treatment. Effect sizes (Cohens *d*) for pre-post differences between and within treatment conditions will be calculated. Following conventions (Cohen, 1988) statistically significant effect sizes ≤ 0.2 will be considered not clinically relevant and for this study a non-inferior difference between conditions.

All analyses will be run allowing for adjustment for stratification variables (i.e. site and diagnosis), and baseline values.

The clinically meaningfulness of results of study will be evaluated calculating numbers and odds ratio for responders and remitted patients using binary logistic regression. 'Responders' are defined as patients receiving a clinically meaningful change in primary outcome, that is ≥ 10 WHO-5 points 'Remission' is defined as patients no longer meeting diagnostic criteria for their primary DSM-5-diagnosis evaluated with the MINI Neuropsychiatric Interview (MINI)²³ 19 weeks after assessment. As an explorative analysis, we will also calculate numbers and odds ratio for patients who no longer met diagnostic criteria for any emotional disorder posttreatment.

Sensitivity analyses

We will run sensitivity analyses for the primary outcome using different definitions of the PP population, depending on how many therapy sessions they attended (i.e. 6, 10 sessions) and using the full ITT-population. Further, we will run a sensitivity analysis without imputed data to assess the potential impact of imputation on the trial findings and assess the impact of missingness by loading the primary analysis using an extreme scenario countering our hypothesis (i.e. imputing the data based on values from the 10% and 90% fractile population). Finally, we will assess the impact of nesting patients in therapy groups by adding therapy group as a random factor. As this analysis might unblind the analyst, this analysis is run after deciphering the blinding.

Additional analyses

Analysis of primary and secondary outcomes will be repeated exploratory at six months follow up.

Differences between groups in clients' evaluation of the therapy post treatment will be evaluated using ANCOVA adjusted for stratification variables and baseline WHO5-values. According to the study protocol (Arnfred et al., 2017)⁷, we intended to assess client satisfaction using the Client Satisfaction Questionnaire²⁴. However, due to problems with the web-based administration of this instrument, the CSQ was not administered systematically. Before data-analysis, we instead decided to use items from the client evaluation questionnaire, which we also administered, developed for '*New Beginnings for patients with Anxiety and Depression*, a Danish lay person guided self-help program' developed in collaboration between Stanford University, the Expert Patients Program Community Interest Company (EPPCIC), the National Health Service, UK and The Danish Committee for Health Education.²⁵ The Questionnaire consists of 13 questions about the client's experiences with the therapy. Items are rated on a five-point Likert scale from 'absolutely agree' to 'absolutely disagree'. The following items were chosen before the blind review as the best items to generally evaluate the therapy: Item 7 'I have become much better at dealing with my symptoms', item 13 'the therapy was worth the time and effort', item 14 'the therapy was very relevant for

my problems'. Frequencies for each item are presented and differences between groups are evaluated using ANCOVA adjusted for stratification variables and baseline WHO5-values.

Subgroup analysis

We will run a confirmative analysis by including interaction terms in the primary analysis model to explore the uniformity of the treatment effect found in the primary analysis across potential subgroups (i.e. stratification variables (site, diagnosis). These results should be interpreted exploratively only, due to the low power for subgroup analyses.

If treatment effects differ across diagnosis, we will conduct supplementary subgroup analysis of primary and secondary outcomes separated by diagnosis.

Adverse events

Adverse events will be listed by group and type of event: (a) Minor adverse events will be reported as number of patients encountering any of these: increasing current medication more than one standard dose step; using according-to-need medication for more than two weeks; increasing current medication to entail more than four types of psychotropic medications; new prescription of supplementary medication (accepted at inclusion); changing previously prescribed antidepressant to another type. (b) Major adverse events will be reported as number of events: New prescription of medication (not accepted at inclusion); contacting psychiatric emergency due to self-injury; suicide attempt without hospitalization; drop-out of therapy due to experienced lack of effect or deterioration. (c) Critical adverse events will be reported as number of events: psychiatric hospitalization due to deterioration or suicide attempt; somatic hospitalization due to self-injury or suicide attempt; referral to electroshock treatment; suicide.

Model checking and validation

We will check the robustness of models by examining residuals.

Handling of missing data and blinding

Data entry is performed by the data manager and research assistants according to the main study protocol. We will undertake a blinded analysis of missing data and outliers to evaluate how to deal with missing data and outliers, and to explore possible predictors of missing data which should be controlled for in the primary and secondary analyses. The analysis of the primary and secondary outcomes will be conducted with the treatment allocation blinded. In the data extraction for the primary analysis, the intervention type is concealed. The intervention and control arm will randomly be coded as '1' and '2'. Deciphering will not be done before all analyses at post-treatment have been performed, and conclusions for the primary outcome has been formulated.

For this analysis plan, we define missing data as those patients with the absence of data at follow-up for one or more outcomes. Data are assumed to be missing at random.

In the primary analysis, the mixed linear regression model handles missing data by full information maximum likelihood, except for the baseline value of WHO-5. Missing baseline WHO-5 values will be handled by multiple imputation with chained equations (m=100) using stratification variables, post-baseline values and variables predicting missing baseline WHO-5 as predictors in the imputation model.

In the secondary analyses, missing data will be handled by multiple imputations with chained equations (m=100) using baseline values of the scales in question, variables predicting missing data, and stratification variables, as auxiliary variables in the imputation models. In cases where other scales are theoretically strongly correlated to the missing data, these scales will also be used as auxiliary variables in the imputation models.

Missing data within a scale less than 25% will be handled by single imputation of mean-scores of the scale. Missingness above 25% within a scale will lead to missing value at scale level and be imputed as described above.

Statistical software

All analyses will be undertaken in SPSS, version 25 and Stata, version 15.^{26,27}

[name]., PhD-fellow, Mental Health Center of Copenhagen, Copenhagen University Hospital, Copenhagen, Denmark

16.8.15

Date

Signature

[name], MSc., statistical consultant, Copenhagen Research Center for Mental Health – CORE, Mental Health Center Copenhagen, Copenhagen University Hospital, Copenhagen, Denmark

Date

Signature

[name] [name]., Post doc, Mental Health Center of Copenhagen, Copenhagen University Hospital, Copenhagen, Denmark

16/08 - 2019

[name]

Date

Signature

[figure not shown]
Principal Investigator [name] [name], PhD, MSc; DMSc, Professor, Psychiatry West, Slagelse, Region Zealand Mental Health Service & Department of Clinical Medicine, Copenhagen University, Denmark

19/8 2019

[Handwritten Signature]

Date

Signature

Error bars indicate 2-sided 95% CIs. The blue dashed line at $x=\Delta$ indicates the noninferiority margin; the blue tinted region to the left of $x=\Delta$ indicates the zone of inferiority. A, If the CI lies wholly to the left of zero, the new treatment is superior. B and C, If the CI lies to the left of Δ and includes zero, the new treatment is noninferior but not shown to be superior. D, If the CI lies wholly to the left of Δ and wholly to the right of zero, the new treatment is noninferior in the sense already defined but also inferior in the sense that a null treatment difference is excluded. This puzzling circumstance is rare, because it requires a very large sample size. It also can result from a noninferiority margin that is too wide. E and F, If the CI includes Δ and zero, the difference is nonsignificant but the result regarding noninferiority is inconclusive. G, If the CI includes Δ and is wholly to the right of zero, the difference is statistically significant but the result is inconclusive regarding possible inferiority of magnitude Δ or worse. H, If the CI is wholly above Δ , the new treatment is inferior.

^³This CI indicates noninferiority in the sense that it does not include Δ , but the new treatment is significantly worse than the standard. Such a result is unlikely because it would require a very large sample size.

^ᵇThis CI is inconclusive in that it is still plausible that the true treatment difference is less than Δ , but the new treatment is significantly worse than the standard. Adapted from Piaggio et al.⁶

Figure 1. From Piaggio, G., Elbourne, D. R., Altman, D. G., Pocock, S. J., Evans, S. J., & CONSORT Group, F. T. (2006). Reporting of noninferiority and equivalence randomized trials: an extension of the CONSORT statement. *Jama*, 295(10), 1152-1160.

	UP (n=)	CBT (n=)	Total (n)= ^a
Patient Characteristics			
Age, mean (SD) years			
Female sex			
Immigrant status (born in Denmark)			
Married/partner			
Children living at home			
Education (profession bachelor/university degree)			
Employment			
Fulltime/part time/student			
Sick leave (≥3 months)			
Retired or job seeking			
Previous episodes with primary diagnosis			
Previous hospitalization			
Previous psychotherapy (min. five sessions)			
Psychotropic medication current			
For YES:			
Antidepressants (SSRI) ^b			
Other ^c			
Age of onset, mean (SD) years			
Comorbid diagnoses			
Any			
At least one depressive or anxiety disorder			

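### The corrected sample size of 208 does not follow from the inputs given for it: they require 218 (220 by the t distribution), and 208 gives about 88.8% power instead of 90%.

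*SAP*

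**What the plan says.** The Sample size section of the SAP first refers to the protocol and then corrects two of its inputs. On the type I error rate it says "the alpha should be 0.025 resulting in a 97.5% one-sided CI", and on variability that "the correct WHO-5 endpoint SD is 20.44", replacing 17.4. The result follows directly: "Using these corrected values, then a sample size of 208 patients are required to be 90% sure that the lower limit" of the one-sided 97.5% interval "will be above the non-inferiority limit of -9 WHO-points".

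The next paragraph raises recruitment from 248 to 320 "to get 204 participants completing the treatment as needed for the primary analysis based on our initial sample size calculations".

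The section gives no true difference, allocation ratio or baseline correlation for the calculation. The closest the SAP comes to a planning difference is its hypothesis: "We hypothesize that subjective well-being and symptom levels will be equally improved following group UP and group dCBT".

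**The concern.** The correction exists to put the sample size and power statement right, and it presents 208 as the consequence of the corrected alpha and SD. Alpha, SD, power and margin all stand in the same paragraph, so a reader should be able to reproduce the figure, and cannot. A trial report that repeats the statement would claim 90% power where the stated inputs give slightly less. The 204-completer target also looks almost sufficient beside 208, but it is 14 short of 218.

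**Working it through.** **Inputs from the SAP, Sample size section**
- One-sided alpha 0.025, so z = 1.95996
- Power 90%, so z = 1.28155
- Endpoint SD 20.44
- Margin 9 WHO-5 points

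**Inputs assumed**
- True difference 0, in line with the hypothesis of equal improvement
- Allocation 1:1 (the SAP leaves randomization to the protocol, which is not at hand)

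**Required total, normal approximation**

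N = 4 × (1.95996 + 1.28155)² × SD² / 9²

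- SD 20.44: 4 × 10.507 × 417.79 / 81 = 216.8, i.e. 109 per arm, 218 in total.
- The noncentral t calculation gives 220.

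The stated 208 is 10 below 218; 218 is 4.8% higher than 208. Before rounding up the gap is 8.8.

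**Attempts to reproduce 208 with SD 20.44 and margin 9**

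| Variant | Total N |
|---|---|
| One-sided alpha 0.05, 90% power | 178 |
| One-sided alpha 0.05, 95% power | 224 |
| One-sided alpha 0.025, 80% power | 162 |
| One-sided alpha 0.025, 88% power | 204 |
| One-sided alpha 0.025, 89% power | 210 |
| One-sided alpha 0.025, 95% power | 270 |
| Equivalence (two one-sided tests), alpha 0.05 | about 223 |
| Equivalence (two one-sided tests), alpha 0.025 | about 268 |

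With the superseded SD of 17.4 and 90% power, alpha 0.025 gives 158 and alpha 0.05 gives 130. None of these is 208. Rounding the SD to one decimal (20.4) gives 215.9, so ordinary rounding does not explain the gap.

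**Inputs that would give 208**
- SD 20.00: 4 × 10.507 × 400 / 81 = 207.6, i.e. 208. Solving for exactly 208 gives SD 20.02.
- True UP advantage of 0.19 points: 216.8 × 9² / 9.19² = 207.9.
- Baseline adjustment with correlation r, where N is multiplied by (1 - r²): r = √(1 - 208/216.8) = 0.20.

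The section states none of these, so which one applies, if any, is inference.

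**Sensitivity to the two assumptions (SD 20.44, 90% power)**
- Allocation 1.5:1 gives 225.8; 2:1 gives 243.9.
- A true UP disadvantage of 0.5 points gives 243.0; a true UP advantage of 0.5 points gives 194.6.

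Unequal allocation therefore only widens the gap. A true difference closes it only if it favours UP.

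**Unadjusted power on the stated inputs**

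Power = Φ(9 / (SD × √(4/N)) - 1.95996)

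For N = 208: SD × √(4/208) = 2.8345; 9 / 2.8345 = 3.175; Φ(3.175 - 1.960) = Φ(1.215) = 88.8%.

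| N | Normal | t |
|---|---|---|
| 204 | 88.2% | 87.9% |
| 208 | 88.8% | 88.5% |
| 218 | 90.2% | 89.9% |
| 220 | 90.4% | 90.2% |

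**The case against.** The strongest objection is that the calculation is only partly visible. The section refers to the protocol and corrects just alpha and SD; the true difference, the allocation and any variance adjustment may be set there. The same simple formula does not reproduce the initial figure either: SD 17.4, one-sided alpha 0.05, 90% power and margin 9 give 130, not 204. Perhaps the protocol used something more.

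This shows that the derivation of 204 cannot be judged from the SAP, and I make no claim about it. It does not rescue 208. If every other input is held fixed, moving to the corrected alpha and SD multiplies N by (20.44/17.4)² × (3.2415/2.9264)² = 1.38 × 1.23, about 1.7. An initial requirement of 204 would then become about 345, not 208. The paragraph also uses a raw endpoint SD and describes no covariate-adjusted calculation.

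A second objection is that unadjusted power is not the power of the planned analysis. The primary analysis is "adjusted for baseline WHO-5 values, variables predictive for missing data, and stratification variables" and uses all 16 WHO-5 measurements. A baseline correlation of about 0.20 at 208, or √(1 - 204/216.8) = 0.24 at 204, would restore 90%. This stands. But patients are treated in groups, and the Sensitivity analyses section says "we will assess the impact of nesting patients in therapy groups by adding therapy group as a random factor"; such clustering would lower power. The SAP quantifies neither effect, so actual power could lie on either side of 90%.

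Third, the effect is slight and little is left to act on: recruitment had already been raised, the blind review had begun, and non-inferiority is decided by the observed interval, not by planned power. That is right as to consequence. It does not make the stated figure correct.

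**Conclusion.** The point holds. On the alpha, SD, power and margin that the SAP names, with zero true difference and 1:1 allocation assumed, the requirement is 218 (220 by t), not 208. Unadjusted power falls short of 90% by 1.2 points at 208 (1.5 by t) and by 1.8 points at 204 completers (2.1 by t). The arithmetic is firm; the origin of 208 is not known, although an SD rounded to 20 would give it exactly. This is a small error in a stated figure, not a material loss of power, and it does not affect the validity of the primary analysis. No claim is made about power after baseline adjustment or clustering.

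**What to change.** In the Sample size section, do one of two things:

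- Restate the requirement for SD 20.44 as 218 by the normal approximation (220 by the t distribution), naming the method and the assumptions of zero true difference and 1:1 allocation. Give the unadjusted power as about 88.8% at 208 and 88.2% at 204 completers, before any gain from baseline adjustment or loss from therapy-group clustering.
- Or keep 208 and state the SD, true difference or baseline correlation that produces it.

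The SAP correctly labels 204 as coming from the initial calculation; adding its power on the corrected inputs would let a reader see how the recruitment target relates to the corrected figure.

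The cost is wording only. Recruitment, data, model, margin and decision rule stay as they are. The one drawback is that, under the first option, the stated power becomes about 88% to 89% instead of 90%.

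### The Sample size section gives two unreconciled requirements, 208 and 204, and 208 does not follow from the SD it cites

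*SAP*

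**What the plan says.** Both statements are in the current SAP (version 2.0), in consecutive paragraphs under Sample size.

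- **Correction paragraph.** The protocol's one-sided 5% alpha and SD of 17.4 are replaced: "the alpha should be 0.025 resulting in a 97.5% one-sided CI" and "the correct WHO-5 endpoint SD is 20.44". With these values, "a sample size of 208 patients are required to be 90% sure" that the lower confidence limit "will be above the non-inferiority limit of -9 WHO-points".
- **Attrition paragraph.** After high attrition in the first year, enrolment was raised from 248 to 320 "to get 204 participants completing the treatment as needed for the primary analysis based on our initial sample size calculations". The section refers to a registered amendment for the revised calculation.

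The section The analysis population takes the primary analysis on patients who received at least eight sessions. The 204 completers are therefore the planned primary-analysis number and can be set directly against 208.

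**The concern.** The first paragraph withdraws two inputs of the initial calculation and states a new requirement. The second justifies the enrolment target by the initial calculation and arrives at a smaller number. A reader cannot tell which figure the trial was meant to reach, or what power the expected completers have at the alpha that the primary analysis will use.

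The decision rule is not at stake, since it depends only on the lower confidence bound and the margin of -9. What is at stake is the power statement that will be carried into the trial report. It matters most if the non-inferiority result is inconclusive and readers ask how likely the trial was to succeed.

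**Working it through.** **Inputs from the SAP (Sample size):** margin 9 WHO-5 points; SD 20.44; one-sided alpha 0.025 (z = 1.960); power 90% (z = 1.2816); stated requirement 208; enrolment 320; completers 204.

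**Assumptions:** 1:1 allocation (the SAP refers to the protocol for randomization); zero true difference (the SAP hypothesises equal improvement); unadjusted two-group comparison; no clustering.

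**1. Try to reproduce 208.** Total N = 4 × [SD × (z for alpha + z for power) / margin]².

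- SD 20.44: 4 × (20.44 × 3.2415 / 9)² = 4 × 7.362² = 216.8, so 109 per arm, **218** in total. With the noncentral t, power is 89.9% at 218 and 90.2% at 220, so about **220**.
- SD 20.0: 4 × (20.0 × 3.2415 / 9)² = 4 × 7.203² = 207.6, so 104 per arm, **208** in total.
- Solving for the SD that 208 implies: 9 × √(208/4) / 3.2415 = 20.02.

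The stated 208 is thus not reproduced from SD 20.44, but it is reproduced from SD 20.0. Other settings at SD 20.44 do not give 208 either: one-sided 0.05 with 90% power gives 178, and one-sided 0.025 with 80% power gives 162.

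**2. Power at each figure.** SE = SD × √(4/N); power = Φ(9/SE − 1.960).

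| Analysed N | SD | SE | Power (normal) | Power (t) |
|---|---|---|---|---|
| 204 | 20.44 | 2.862 | 88.2% | 87.9% |
| 208 | 20.44 | 2.834 | 88.8% | 88.5% |
| 218 | 20.44 | 2.769 | 90.2% | 89.9% |
| 204 | 20.0 | 2.801 | 89.5% | not computed |

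**3. Split the shortfall at SD 20.44.** From 90% to 88.8% is 1.2 points, which arises because 208 is too low for that SD. From 88.8% to 88.2% is 0.6 points, which arises from 204 in place of 208. The total is 1.8 points.

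**4. Enrolment at the implied retention.** 204/320 = 63.75%, an attrition of 36.25%. Then 208 completers correspond to 208/0.6375 = 326.3, or 327 enrolled, and 218 completers to 218/0.6375 = 341.96, or 342 enrolled, against the planned 320.

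**5. Effect of baseline adjustment.** The SAP gives no baseline–endpoint correlation r. Replacing SD by SD × √(1 − r²) at 204 completers gives 89.4% for r = 0.2, 90.9% for r = 0.3 and 95.3% for r = 0.5. Clustering by therapy group acts in the other direction, but the SAP gives no intraclass correlation, so its effect cannot be calculated.

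**The case against.** The strongest reply is that the attrition paragraph records a past decision and says openly that 320 rested on the initial calculation. The SAP attaches 90% power only to 208 and never claims it for 320 or 204. The difference between 204 and 208 is four patients, and the planned analysis is a mixed model with baseline adjustment and repeated WHO-5 measurements, not the simple comparison behind these figures. All of this stands. It is why the history should stay in the text and why the consequence is small. It does not reconcile the two paragraphs, and it does not make 208 follow from SD 20.44.

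A reader might infer three stronger things that the document does not support.

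- **That choosing 204 over 208 costs about two points of power.** It costs about 0.6. The rest comes from 208 itself.
- **That the trial fails to reach 90% power in its planned analysis.** This is not shown. A baseline correlation of about 0.24 would restore 90% at 204 in the simple calculation, clustering could take it away again, and the SAP quantifies neither.
- **That 204 is wrong even by the initial calculation.** The SAP does not give the power used there and leaves that calculation to the protocol, so this cannot be tested.

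**Conclusion.** The point holds as a small inconsistency in the sample-size statement, with a recomputation attached. The section gives 208 and 204 as requirements without reconciling them and bases the enrolment target on inputs it has just replaced. The larger part of the discrepancy is that the cited SD of 20.44 needs about 218 analysed patients (220 by t), 10 more than stated, and that 208 corresponds to an SD of 20.0.

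Under the corrected inputs, 204 completers give about 88% power, 1.8 points below 90% by the normal approximation and 2.1 by the t distribution. These figures rest on 1:1 allocation, zero true difference and an unadjusted, unclustered comparison. They do not show that the trial is materially underpowered, and they do not affect the analysis or the non-inferiority rule.

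**What to change.** Make both changes in one edit. If only the second paragraph were changed, 208 with 90% would stand beside 204 with 88%, which no single SD can produce.

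- **Correction paragraph:** recompute the requirement from the cited inputs (about 218, or 220 by t), or state the SD actually used to obtain 208.
- **Attrition paragraph:** keep the account of how 320 was chosen and add wording such as: *Enrolment of 320 was set using the initial calculation. With the implied attrition of about 36% we expect 204 completers. At one-sided alpha 0.025, SD 20.44 and margin 9 this gives about 88% power for an unadjusted comparison, assuming 1:1 allocation and no true difference, before any gain from baseline adjustment or loss from clustering by therapy group.*

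If a different SD is stated for 208, recalculate the power at 204 with that SD (about 89.5% at SD 20.0).

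The cost is a few sentences and a slightly less favourable power figure. Enrolment and the analysis stay as they are. The SAP's Introduction allows adjustments up to the breaking of the blind.
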